9.2. General Statistical Considerations

Statistical analysis of this study will be the responsibility of Lilly.

For the Phase 1a, a 3+3 design will be used to assess the safety of ramucirumab in combination with pembrolizumab (Section 6.1.1.1). Additional patients will be enrolled in a dosing schedule to achieve the minimum of 3 evaluable patients, if dropouts or dose interruptions or reductions occur that result in a patient being non-evaluable for DLTs. Data will be reviewed by dose schedule group (3 patients).

The final analysis of safety and preliminary efficacy will occur approximately 2 years after the first patient received first study treatment. Separate interim analyses will occur after all patients in each cohort have completed approximately 24 weeks of study treatment or discontinued for any reason. Safety and preliminary efficacy will be analyzed separately for each cohort (details in Section 9.8).

Descriptive statistics will be derived where appropriate. The rate of DLTs will be summarized by cohort; dose exposure and density for each study drug will be calculated by each cohort.

Pharmacodynamics/Biomarkers

Pharmacodynamic and/or tailoring biomarker analyses will be based on the subset of patients from the above cohorts from whom a valid assay result (according to laboratory guideline) has been obtained.

General

Additional details will be provided in a separate statistical analysis plan (SAP) for the study. Any change to the data analysis methods described in the protocol will require an amendment ONLY if it changes a principal feature of the protocol.

Additional exploratory analyses of the data will be conducted as deemed appropriate.

9.3. Patient Characteristics

Patient characteristics which will be summarized by cohort:

- Patient demographics will be reported using descriptive statistics. Demographic data are collected and reported to demonstrate that a trial population represents the target patient population considered for regulatory approval.
- Baseline disease characteristics will be summarized by presenting frequency counts and percentages (for example, for pathological diagnosis [histological or cytological] and disease stage).
- A detailed description of patient disposition will be provided. It will include a summary of the number and percentage of patients entered into the study, enrolled in the study, and treated as well as number and percentage of patients completing the study, or discontinuing (overall and by reason for discontinuation).
- Disease-related therapies, including prior anticancer treatments, prior radiotherapies (such as type of therapy, regimen, and prior surgery)

Other patient characteristics will be summarized as deemed appropriate.

9.3.1. Concomitant Therapy

Concomitant medications will be summarized for the safety population.

9.3.1.1. Postdiscontinuation Therapy

The numbers and percentages of patients reporting postdiscontinuation therapies will be provided overall, by type of therapy (surgery, radiotherapy, or systemic therapy), and by drug name.

9.3.2. Treatment Compliance

The number of dose omissions, reductions, and delays, number of cycles received, and dose intensity will be summarized for all treated patients and for both study drugs.

9.4. Efficacy Analysis: Phase 1b

The objective response rate and disease control rate, and the corresponding confidence interval, will be provided by cohort (according to RECIST v1.1 and irRECIST). Time-to-event variables, such as time to response, duration of response, PFS, and OS will be estimated by Kaplan-Meier (1958) methodology by cohort. Presentations of efficacy may include patients enrolled in DLT Phase 1a with the same tumor type and treatment schedule.

Individual changes in the tumor burden over time will be presented graphically within a tumor type (that is, Waterfall plots). Subgroup analysis of interest will be further defined in the SAP. Association between tumor PD-L1 expression at baseline will also be correlated with clinical outcomes such as overall response rate, and further assessed and characterized by appropriate statistics.

9.5. Safety Analyses

All patients who receive at least 1 dose of ramucirumab or pembrolizumab will be evaluated for safety and toxicity. Adverse event terms and severity grades will be assigned by the investigator using CTCAE, Version 4.0.

Safety analyses will include summaries of the following:

- DLTs: the number of patients who experienced any DLTs during Cycle 1 will be summarized by dose schedule in Phase 1a
- AEs, including severity and possible relationship to study drug
- AEs by MedDRA System Organ Class (SOC) by decreasing frequency of Preferred Term within SOC
- Laboratory and nonlaboratory AEs by CTCAE term and maximum CTCAE grade (regardless of causality and at least possibly related to study treatment)

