6.1. Treatments Administered

Ramucirumab and pembrolizumab will be administered per [Table JVDF.2](#). For Gastric/GEJ, Urothelial, 2nd-4th line NSCLC and BTC, patients can receive study treatment after evaluable tumor tissue has been shipped to central study laboratory. For first line NSCLC, patient can receive study treatment after PD-L1 expression has been confirmed to be at least 1% (Section [5.1](#)).

Across all study periods, including the continued access period, individual patients will be treated with ramucirumab and/or pembrolizumab, as follows:

- until confirmed progressive disease (Section [8.1.1.3](#)), unacceptable toxicity, or discontinuation for any other reason
- for a maximum duration of study treatment of 35 cycles, approximately 2 years

Table JVDF.2. Phase 1 Treatment Regimens/Dosing Schedule

Tumor Type	Drug	Dose (IV)	Dose Frequency	Dose Day (21-day cycle)
Schedule 1 (Gastric-GEJ, BTC)	Ramucirumab	8 mg/kg	Q3W	Day 1, Day 8
	Pembrolizumab	200 mg	Q3W	Day 1
Schedule 2 (Gastric-GEJ, NSCLC or Urothelial)	Ramucirumab	10 mg/kg	Q3W	Day 1
	Pembrolizumab	200 mg	Q3W	Day 1

Abbreviations: BTC = biliary tract cancer; GEJ = gastroesophageal junction; IV = intravenous; NSCLC = non-small cell lung cancer; Q3W = every 3 weeks.

NOTE: Ramucirumab will be administered prior to pembrolizumab for every cycle (Section [6.1.1](#)).

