5.2.1.3. Adverse Event-Related Variables

Adverse event-related variables are listed below:

- **Dose-limiting toxicity (DLT):** Please refer to Section 5.2.1.1 for the definition of DLT.
- **Adverse event (AE)** is defined as any untoward medical occurrence in a patient administered a pharmaceutical product, without regard to the possibility of a causal relationship.
- **Treatment-emergent adverse event (TEAE)** is defined as an event that first occurred or worsened in severity between first dose of study treatment and 90 days after the last dose of study treatment and related SAEs reported beyond 90 days after the last dose of study treatment, where last dose stands for actual dose, that is, 0 dose is not counted as last dose.
- **Adverse events of special interest (AESIs)** for ramucirumab include arterial thromboembolic events (ATEs)*, congestive heart failure (CHF)*, fistula (gastrointestinal [GI]* and non-GI), gastrointestinal perforation (non-fistula)*, hemorrhage (also GI hemorrhage as a subcategory and pulmonary hemorrhage [composite term])*, healing complication, hypertension*, infusion-related reaction (IRR) including anaphylactic reaction, liver injury/failure*, proteinuria*, reversible posterior leukoencephalopathy syndrome (RPLS), and venous thromboembolic events*.

Notes:

1. All AESIs are compound level.
2. Each AESI is defined by a set of MedDRA preferred terms (PTs).
 - 2.1. For RPLS, the PTs were directly selected from MedDRA.
 - 2.2. For AESIs marked with *, the PTs were selected from the applicable standardized MedDRA queries (SMQs) v.15.0 or higher.
 - 2.3. For non-GI fistula, all PTs containing the text string “fistula” need be used for analysis.
 - 2.4. For the rest of the AESIs, the PTs were identified through medical review of all unique PTs collected in all ramucirumab studies for compound-level AESIs.
3. Categories of AESIs may be modified as the understanding of the safety of the investigational drug increases. The final list of categories will be reported in the clinical study report (CSR).

- **Consolidated AEs** include abdominal pain, anemia, fatigue, hyperbilirubinaemia, hypercalcaemia, hyperkalaemia, hypermagnesaemia, hypernatraemia, hyperphosphataemia, hypoalbuminaemia, hypocalcaemia, hypokalaemia, hypomagnesaemia, hyponatraemia, hypophosphataemia, intestinal obstruction, leukopenia, myocardial infarction, neuropathy, neutropenia, rash, renal failure, thrombocytopenia, and urticarial.

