5.3. Description of Analysis

5.3.1. General Consideration

All data, including derived data, will be listed for all enrolled subjects by study phase, assigned LY3009806 dose, cohort, patient number, cycle, and time point where appropriate, unless stated otherwise in the following text or in the table shells.

In the Phase 1a part of the study, data will be summarized by assigned ramucirumab + pembrolizumab dose levels and schedules for preliminary analysis unless stated otherwise.

Note: 2 dose schedules of ramucirumab were considered for the Phase 1a part of the study. In addition, data may be summarized by the same indication and dose schedule in combination with the Phase 1b part of the study. They are:

- 2L-3L Gastric (Schedule1): Cohort A + Phase 1a patients with same indication/dose schedule/level as Cohort A
- 2L-3L Gastric (Schedule2): Cohort B + Phase 1a patients with same indication/dose schedule/level as Cohort B
- 2L-4L NSCLC: Cohort C + Phase 1a patients with same indication/dose schedule/level as Cohort C
- 2L-4L Urothelial: Cohort D + Phase 1a patients with same indication/dose schedule/level as Cohort D
- 2L-3L Gastric (total): 2L-3L Gastric Schedule 1 + 2L-3L Gastric Schedule 2

In general, continuous variables will be presented using the mean, standard deviation, median, minimum, maximum, and number of patients with an observation (n).

For categorical variables, the population size (N), the number of events, the number of subjects with events (n), and the proportion of subjects with events ($p=n/N$) are usually reported.

Additional exploratory analyses of the data will be conducted as deemed appropriate.

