5.3.7. Safety Analyses

All patients who receive at least one dose of study therapy will be summarized for safety and toxicity.

Dose-limiting toxicities will be listed for the Phase 1a part of the study only by ramucirumab dose schedule.

The most current version of MedDRA at time of analysis will be used when reporting AEs by MedDRA terms. The NCI CTCAE Version 4.0 will serve as the reference document for choosing appropriate terminology for, and grading the severity of, all AEs and other symptoms. Unless otherwise specified, when summarized by PT, AEs will be presented in decreasing frequency of PT across treatment arms; when summarized by system organ class (SOC) and PT, AEs will be presented in decreasing frequency of PT within SOC across treatment arms. If more than 1 AE is recorded for a patient within any SOC or PT term, the patient will only be counted once on the most severe grade and the closest relationship to treatment. A patient listing of all AEs will be provided.

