5.3.7.1. Treatment-Emergent Adverse Events

Treatment-emergent adverse events will be summarized by decreasing frequency of SOC by PT and by CTCAE grade regardless of causality and related to any study drug separately. Note, “by CTCAE grade” refers to the categories of all grade, Grade 3-4, and Grade 3-5. Consolidated TEAEs will also be summarized.

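### TEAE, SAE and AESI summaries are crude patient percentages over observation time that grows with time on treatment, with no time-based summary alongside

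*Protocol*

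**What the plan says.** - **Measure.** SAP 5.3.1 reports for categorical variables "the population size (N), the number of events, the number of subjects with events (n), and the proportion of subjects with events". The denominator is a head count.
- **Counting rule.** Under SAP 5.3.7, when a patient has several events within a term, "the patient will only be counted once on the most severe grade and the closest relationship to treatment". The same section orders the tables by frequency across treatment arms.
- **Tables.** SAP 5.3.7.1 states "Treatment-emergent adverse events will be summarized by decreasing frequency of SOC by PT and by CTCAE grade regardless of causality". SAP 5.3.8 tabulates SAEs and AESIs by preferred term, with SAEs to 30 and to 90 days after therapy. Protocol 9.5 lists "AEs by MedDRA System Organ Class (SOC) by decreasing frequency of Preferred Term within SOC".
- **Who is included.** Protocol 9.5: "All patients who receive at least 1 dose of ramucirumab or pembrolizumab will be evaluated for safety and toxicity". One dose is enough.
- **How long.** Protocol 6.1 treats to confirmed progression or toxicity, "for a maximum duration of study treatment of 35 cycles, approximately 2 years". SAP 5.2.1.3 counts as treatment-emergent an event starting or worsening "between first dose of study treatment and 90 days after the last dose of study treatment", plus later related SAEs.
- **Exposure.** SAP 5.3.6 summarizes treatment duration and infusions in separate tables. Ramucirumab exposure and safety may be explored (Protocol 9.6, SAP 5.3.12), but that is optional and belongs to the PK analyses.

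**The concern.** The primary objective is the safety and tolerability of two dosing regimens. A crude percentage combines the risk per unit of time with the time observed. If one cohort stays on treatment longer than another, for example a first-line cohort against a later-line one, more of its patients will show an event even at equal monthly risk. A cohort that stops early can look safer than it is.

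The cohorts differ in tumor type, line and schedule together. Biliary and first-line gastric patients are all on Schedule 1; NSCLC and urothelial patients are all on Schedule 2. The safety results help decide whether to expand or to test other doses and schedules (Protocol 4.1). The plan uses Kaplan-Meier methods for secondary time-to-event efficacy endpoints but no time-based method for TEAEs, SAEs or AESIs.

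**Working it through.** **Range of exposure.** 35 cycles × 21 days = 735 days = 105 weeks = 24.1 months, which reproduces the protocol's figure of about 2 years. The minimum is one dose.

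**Inputs from the documents.** There is no expected time on treatment for the combination, so median PFS of other regimens serves as a proxy:

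| Setting (Protocol section 2, including Table JVDF.1) | Median PFS |
|---|---|
| Gastric, ramucirumab alone | 2.1 months |
| Gastric, ramucirumab + paclitaxel | 4.4 months |
| NSCLC, ramucirumab + docetaxel | 4.5 months |
| Urothelial, ramucirumab + docetaxel | 5.1 months |
| Urothelial, pembrolizumab alone | 8.6 weeks (2.0 months) |
| First-line gastric/GEJ/cardia, ramucirumab + mFOLFOX-6 | 8.7 months |

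**Assumptions.** Constant AE hazard L, the same in every cohort (0.02, 0.05 or 0.10 per month); exponential time on treatment with m = ln 2 / median, capped at M = 24.1 months; follow-up tail w = 90 days = 2.96 months.

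**Formula.** Crude proportion = 1 − exp(−L·w) × E, where E = [m/(L+m)] × [1 − exp(−(L+m)M)] + exp(−(L+m)M).

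Example, L = 0.05 and median 4.4 months: m = 0.1575; E = 0.7591 × 0.9933 + 0.0067 = 0.7607; exp(−0.05 × 2.96) = 0.8626; crude = 1 − 0.8626 × 0.7607 = 34.4%.

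| Median (months) | L = 0.02 | L = 0.05 | L = 0.10 |
|---|---|---|---|
| 2.0 | 10.8% | 24.5% | 42.1% |
| 2.1 | 11.1% | 25.1% | 42.9% |
| 4.4 | 16.2% | 34.4% | 54.4% |
| 4.5 | 16.4% | 34.7% | 54.8% |
| 5.1 | 17.6% | 36.7% | 57.0% |
| 8.7 | 23.0% | 45.6% | 66.5% |

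With a 30-day tail, the collection period for non-serious AEs, the L = 0.05 figures at 2.1, 4.5 and 8.7 months are 17.3%, 28.0% and 39.9%. For individual patients at L = 0.05 with the 90-day tail, the probability is 16.7% after one cycle and 74.2% after 35.

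**Like for like.** The 2.1-month gastric figure is ramucirumab alone; the 4.5 and 5.1 are ramucirumab plus docetaxel. For ramucirumab plus a taxane the medians are 4.4, 4.5 and 5.1, giving 34.4%, 34.7% and 36.7% at L = 0.05. The two single-agent figures, 2.1 and 2.0 months, give 25.1% and 24.5%. Most of the apparent spread between tumor types comes from mixing regimens.

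**By schedule** (L = 0.05, 90-day tail, weighted by planned cohort size). Cohorts A and B at 2.1 months, A2 at 8.7, C at 4.5, D at 2.0; A1 and E, which have no usable figure, each varied from 2.1 to 8.7. Schedule 1 (n = 65) runs from 33.0% to 40.8%, Schedule 2 (n = 90) from 27.6% to 33.3%. The difference, Schedule 1 minus Schedule 2, runs from 33.0 − 33.3 = −0.3 to 40.8 − 27.6 = 13.2 points. Cohort A against B at equal duration: 25.1% against 25.1%.

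**After the fix.** Under the same assumptions at L = 0.05, simulation of patients with a first event divided by patient-months at risk gives 0.0498 to 0.0502 per month for medians from 2.0 to 8.7. The estimates are imprecise: the standard deviation is about 0.016 to 0.021 at n = 25 and 0.027 at n = 15.

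**The case against.** **The size rests on a proxy.** The hazards are assumed and PFS under other regimens is not time on this combination. Patients may stay on treatment past first radiologic progression while confirmation is awaited (Protocol 8.1.1.3) or stop earlier for toxicity. This stands, and with comparable medians the artifact nearly vanishes.

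**Two stronger readings are not supported.** A reader might infer that the two regimens will show different AE rates even at equal risk. The direct contrast is Cohort A against B, same tumor type and line, and there is no artifact unless their durations or follow-up differ. A reader might also infer that crude tables hide excess toxicity of Schedule 1. The direction is not determined; in the pooled illustration Schedule 1 looks about the same or worse.

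**Not every AE summary is affected.** DLTs, a named primary endpoint, use a fixed 21-day window. The registry output (SAP 5.3.16) adds event counts, though its at-risk figure is still a number of participants.

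**Safety is descriptive.** Cohorts are analyzed separately, no AE test across them is planned, and duration and dose intensity are reported. That lowers the stakes. But summary durations beside a crude percentage do not let a reader recover a rate or a cumulative incidence, and ordering tables across arms invites side-by-side reading.

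**Little precision is gained at n = 15 to 25.** True; this is a reason for intervals and for limiting the additions to a few categories.

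**Conclusion.** The general TEAE, SAE and AESI tables are crude proportions over unequal observation time, and no time-based summary is planned. Where time on treatment differs between cohorts, equal monthly risk can give clearly different percentages: at 0.05 per month with a 90-day tail, about 25%, 35% and 46% at medians of 2.1, 4.5 and 8.7 months. At 4.4 against 4.5 months the gap is 0.3 points. These figures assume a constant, equal hazard, exponential time on treatment and PFS as a proxy, so they illustrate a possible bias and do not predict one. The documents do not determine which schedule would be favored. This is a worthwhile, inexpensive reporting improvement; it does not invalidate the safety analysis.

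**What to change.** Keep the crude tables. In SAP 5.3.7 and 5.3.8, with a matching line in Protocol 9.5, add for Grade 3 or higher TEAEs, SAEs and AESIs, by cohort and dose schedule:

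1. **Common early window.** The proportion with a first event within, for example, 24 weeks of first dose, the point to which the interim analyses are tied. Estimate it by cumulative incidence with death as the competing event, or with stopping treatment as the competing event if the analysis is on-treatment only. Counting stopping as a competing event under the full TEAE definition would discard post-treatment events that the SAP counts.
2. **Rate.** Patients with a first event per 100 patient-months at risk, with an exact Poisson confidence interval.

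At-risk time must match what is collected. Protocol Table JVDF.7 collects all AEs to 30 days after stopping and all SAEs to the 90-day visit; Protocol 8.2.1.2 shortens SAE collection when new anticancer therapy starts. SAP 5.2.1.3 applies one 90-day TEAE window. These passages should be reconciled and the at-risk end date stated for each event class.

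The cost is SAP text and a few table columns; AE onset and dosing dates already enter SAP derivations. Intervals will be wide at n = 15 to 25. The rate assumes a constant hazard and can mislead for early events such as infusion reactions, so the common-window table should accompany it.

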9.6. Pharmacokinetic/Pharmacodynamic Analyses

The sampling schedule for drawing blood samples for ramucirumab PK is provided in [Attachment 2](#). Serum concentrations of ramucirumab prior to infusion (C_{\min}) and at 1 hour after the end of the ramucirumab infusion (approximately maximum concentrations) will be summarized using descriptive statistics.

Population PK analyses for ramucirumab may be conducted using population PK approach. The relationship between ramucirumab exposure and selected safety outcomes may be explored.

9.7. Other Analysis

9.7.1. *Immunogenicity*

Immunogenicity (anti-ramucirumab antibody) incidence will be tabulated, and correlation to ramucirumab drug level, activity, and safety will be assessed, as appropriate, respectively. The measures that will be analyzed include baseline presence and level of ADA, treatment-emergent ADA, levels of neutralizing ADA, and incidence and levels of ADA related to IRRs.

9.7.2. *Biomarker Analysis*

Biomarkers will be summarized and assessed for correlations with clinical outcomes. Biomarker relationships by tumor type, changes in biomarker levels over time, and differences among dose levels or exposure will be explored as possible.

9.8. Interim Analyses

For Phase 1a, safety and PK data will be reviewed on a cohort-by-cohort basis during the study. The purpose of these data reviews is to evaluate the safety and tolerability for each dose schedule and determine if a DLT has been observed. The investigators and the Lilly study team will evaluate the totality of data to determine whether or not to move into the Expansion Phase 1b.

Separate interim analyses will occur after all patients in each cohort have completed approximately 24 weeks of study treatment or discontinued for any reason. The interim analyses may be combined if they are expected to occur within approximately a month, and interim analyses may also be combined with the ongoing trial-level safety review or annual safety review for annual safety update reporting.

An independent data monitoring committee may be initiated if one or more additional cohorts will be expanded to further explore safety and efficacy for the ramucirumab and pembrolizumab combination.

10. Regulatory and Ethical Considerations, Including the Informed Consent Process

10.1. Informed Consent

The investigator is responsible for ensuring that the patient understands the potential risks and benefits of participating in the study, including answering any questions the patient may have throughout the study and sharing in a timely manner any new information that may be relevant to the patient's willingness to continue his or her participation in the trial.

The ICF will be used to explain the potential risks and benefits of study participation to the patient in simple terms before the patient is entered into the study, and to document that the patient is satisfied with his or her understanding of the risks and benefits of participating in the study and desires to participate in the study.

The investigator is responsible for ensuring that informed consent is given by each patient or legal representative. This includes obtaining the appropriate signatures and dates on the ICF prior to the performance of any protocol procedures and prior to the administration of investigational product.

